4.2.5 Day of SRS

- 4.2.5.1** Documentation of corticosteroid use/no dexamethasone (or any other corticosteroid with the purpose of treating cerebral edema) use.

4.2.5.2 Continued fingerstick glucose draws by patient once a day (in the morning before breakfast [fasting]) for at least 1 week after SRS. Please see section 5.4.2 for further details.

4.2.6 1 week after SRS (± 3 days)

4.2.6.1 Review the patient's blood glucose and medication administration logs.

4.2.6.2 CBC with differential and CMP including LFTs.

4.2.6.3 Fingerstick Glucose draw by nurse/research team member.

4.2.6.4 Adverse event evaluation. If no "*concerning toxicity*" or "*serious toxicity*" (see section 5.3.2), then patient will be instructed to discontinue blood glucose monitoring.

4.2.6.4.1 If the patient does have a "*concerning toxicity*" or "*serious toxicity*" they must discontinue their investigational medication (see section 5.3.2) and thus can also discontinue with fingerstick glucose draws.

4.2.6.5 Documentation of corticosteroid use (record the date of initiation, dose and reason for initiation of any new corticosteroid, especially dexamethasone).

4.2.7 1 month after SRS (- 5 or + 10 days)

4.2.7.1 Discontinue investigational medication (last dose is taken the evening of obtaining the follow-up MRI). Have patient return all remaining (untaken) investigational medication tablets.

4.2.7.2 Follow-up brain MRI with and without contrast. T1-weighted, T2, and/or FLAIR MRI of the brain (maximum slice thickness 5mm). FLAIR imaging is preferred.

4.2.7.2.1 T1 post gadolinium sequence will be imported into the Eclipse treatment planning system and the radiation oncologist (who will be blinded to the patient's investigational medication) will contour the enhancing tumor that received the prescribed dose of SRS.

4.2.7.2.2 FLAIR sequence will be imported into the Eclipse treatment planning system. FLAIR volume will be automatically calculated using "Region Growing" on Eclipse (Appendix I). The automated contours will be verified and modified as needed by the radiation oncologist who will be blinded to the patient's investigational medication.

4.2.7.3 Follow-up history and physical with neurologic examination and corticosteroid use documentation (record the date of initiation, dose and reason for initiation of any new corticosteroid, especially dexamethasone). A last fingerstick glucose draw will be done by the nurse/research team member.

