Appendix VII for Adverse Event (AE) definitions and grading scale information.

If multiple toxicities are seen, the presence of a DLT should be based on the most severe toxicity experienced. Any patient who achieves a DLT will be taken off of the investigational medication immediately, but will still be evaluable.

Concerning Toxicity

1. Any **asymptomatic grade 3 or 4 hypoglycemia** as defined by CTCAE version 4.0.
2. Any **non-hematologic grade 3 or greater toxicity** (including neurologic toxicity) that is associated with a blood glucose level ≤ 80 mg/dl and is resolved with "low blood sugar intervention" (e.g. a return of blood glucose level to ≥ 80 mg/dl).

Serious Toxicity

1. Any **grade 5 toxicity** that is deemed by the investigator to be **at least possibly attributable to the investigational medication**.
2. Any **symptomatic grade 3 or 4 hypoglycemia** that is associated with a **non-hematologic grade 3 or greater toxicity** that is not resolved with “low blood sugar intervention” (e.g. does not return to blood glucose level of ≥ 80 mg/dl) that is deemed by the investigator to be **at least possibly attributable to the investigational medication**.

Investigational medication will be discontinued for any patient that meets the criteria for a “concerning toxicity” or “serious toxicity”. These patients will still be evaluable. All other patients currently on treatment at the time may continue with their current investigational medication without interruption.

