7.2 Randomized Portion

7.2.1 Non-Micronized glyburide (1.25 mg po BID) or placebo (1 tablet po BID) should be administered orally twice a day beginning at least 5 days prior to SRS. The investigational medication will be taken in the morning with breakfast and in the evening with dinner. All patients and the study team will be blinded to the investigational medication which will continue until the evening dose on the day of the one month post SRS follow-up MRI. If the patient misses a dose at any time, it will not be made up. All doses (whether missed or taken) should be recorded in the medication administration log.

7.2.1.1 In the event of a DLT in the Pilot Portion requiring a dose reduction and this dose is considered safe, patients will receive either a reduced dose of non-micronized glyburide (now at 0.75 mg po BID) or the placebo (1 tablet po BID). The investigational medication will be taken in the morning with breakfast and in the evening with dinner. All patients and the study team will be blinded to the investigational medication which will continue until the evening dose on the day of the one month post SRS follow-up MRI. If the patient misses a dose at any time, it will not be made up. All doses (whether missed or taken) should be recorded in the medication administration log.

7.2.2 In the event of a DLT in the Randomized Portion of the study, the patient who experienced the DLT will stop their investigational medication immediately. Other patients currently on study at the time of the DLT will continue on study treatment without interruption.

7.2.3 If a patient suffers a DLT (either a “*concerning toxicity*” or a “*serious toxicity*”) after registration but before SRS, he/she will be removed from the protocol and considered inevaluable.

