7.3.3 Toxicity Reporting

The research team and the treating physicians/Principal Investigator will review the toxicities and record them in OnCore. Attribution of toxicity to protocol and clinical relevance will be reviewed.

If a dose limiting toxicity (DLT) or other significant medical event is unexpected and probably related to study treatment, then it will be submitted to the UAB IRB via the Problem Report form. All adverse events entered into OnCore will be submitted for review on an annual basis.

Patients that are withdrawn from the study after beginning protocol treatment will be followed for adverse events for 30 days after last dose of glyburide or investigational medication.

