7.6 Guidelines and Procedure for Unblinding Treatment (Randomized Portion)

The site/treating physician may request to unblind their patient's treatment randomization only under specific circumstances. All must be done to ensure the blind. The following circumstances would be deemed appropriate for unblinding:

- A life-threatening event or extraordinary clinical circumstance in which knowledge of the drug assignment will affect clinical judgment.

7.6.1 The unblinding procedure is outlined below. All parties must strictly adhere to the procedure in order to maintain protocol integrity and protect the blind.

1. The requesting physician will call and/or email the research team to request the unblinding of their patient.
2. The requesting physician will provide the case number, reason and appropriate details for the request of unblinding.
3. The research team will then determine after consulting with the PI of the study if unblinding is appropriate in the specific case addressed. If unblinding is denied, the reason will be provided in a timely fashion to the requesting physician. An appeal can be made by the requesting physician if appropriate.
4. If approved for unblinding, the IDS pharmacy is contacted by the research team.
5. The IDS pharmacy may be in direct contact with the requesting physician or the research team/PI may be asked to relay the unblinded information to the requesting physician.

All discussions and outcomes of a blinding request will be well documented in the patient's chart as well as in the research office. All research staff involved in the unblinding activity for this protocol should continue to remain blinded to drug assignment/randomization if possible.

7.6.2 The research office will notify the UAB IRB and UAB Clinical Trials Monitoring Committee (CTMC) of patient unblindings at the time of the annual protocol review. If appropriate and fitting the criteria of the Problem Report form, appropriate steps will be taken for reporting.

7.6.3 Unblinded patients will be taken off study treatment and followed for 30 days after last dose of investigational medication, irrelevant to the date of unblinding.

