9.0 STATISTICAL CONSIDERATIONS

9.1 Definition of primary outcome/endpoint

9.1.1 Pilot Portion: Occurrence of Dose Limiting Toxicities (DLTs) between the time of glyburide initiation and the time of the one month follow-up MRI.

9.1.2 Randomized Portion:

Each eligible patient will be evaluated for treatment outcome as success or failure, as defined later in this section. Each patient's treatment outcome will be associated with randomized regimen regardless of the treatment the patient actually receives. A treatment failure will be considered to have occurred if edema increases sufficiently to require the initiation of dexamethasone (or any corticosteroid administration with the purpose of treating cerebral edema) between the time of SRS* and the time of the one month follow-up MRI, or the patient dies in that same interval from a cause considered probably or likely related to Glyburide. Otherwise, the patient will be considered to have experienced treatment success.

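### Follow-up of unblinded and withdrawn patients is timed from the last dose, so it never has to reach three months, can miss the one-month outcome, and 9.1.2 would score an unseen failure as success

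*Combined protocol and SAP*

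**What the plan says.** Two rules time follow-up from the last dose. Section 7.6.3 states: "Unblinded patients will be taken off study treatment and followed for 30 days after last dose of investigational medication", whatever the date of unblinding. Section 7.3.3 states: "Patients that are withdrawn from the study after beginning protocol treatment will be followed for adverse events for 30 days after last dose". The second covers adverse events and mentions neither corticosteroid documentation nor MRI.

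The endpoints are timed from SRS. Section 9.1.2 assigns each eligible patient to the randomized regimen whatever treatment was received. Failure is corticosteroid started for cerebral edema, or a death probably or likely related to glyburide, between SRS and the one-month MRI. It then adds: "Otherwise, the patient will be considered to have experienced treatment success". Sections 4.2.7 and 4.2.8 place the one-month visit at -5 to +10 days and the three-month visit at -10 to +14 days; Appendix VIII gives the nominal days as 30 and 90. The secondary endpoints in 9.2.2 for steroid initiation, edema and tumor volume use both visits.

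Drug stopping and evaluability are dealt with separately for toxicity. Section 5.3.2 says: "Any patient who achieves a DLT will be taken off of the investigational medication immediately, but will still be evaluable". The stated grounds for inevaluability all arise before or at SRS: steroid started before SRS (4.2.9.2, 8.2.1), DLT before SRS (7.2.3), and removal at SRS planning, including SRS not being deliverable (6.1). Nothing says how a patient unblinded or withdrawn after SRS is classified.

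**The concern.** A patient analysed by randomized arm should be observed for the whole outcome interval, whatever happens to study drug. Here two groups who leave treatment early have a follow-up period tied to a different event. If observation ends before the one-month MRI, or does not include steroid use, a steroid start can go unrecorded, and the closing sentence of 9.1.2 then makes the patient a success.

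The go/no-go rule rests on 20 patients per arm, so each patient is 5 percentage points of the success rate. Losses that were more frequent on one arm would move the decision towards that arm. There is also an inconsistency: a patient who stops drug for a DLT after SRS stays evaluable on the usual schedule, but if the same event leads to unblinding, 7.6.3 sets a different follow-up.

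**Working it through.** **Inputs.** Dosing "should be administered orally twice a day beginning at least 5 days prior to SRS" (7.2.1), with drug dispensed 5 to 9 days before SRS (4.2.4), so the earliest possible dose is day -9. For the latest dose, 4.2.7.1 says the "last dose is taken the evening of obtaining the follow-up MRI". Windows, with SRS as day 0: one month is 30 - 5 = 25 to 30 + 10 = 40; three months is 90 - 10 = 80 to 90 + 14 = 104. There are 20 patients per arm, with a one-sided exact test at 0.30 (9.3.2) and expected success of 50% on placebo and 75% on glyburide (9.5.2).

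**Timing.** Required follow-up ends on day d + 30, where d is the day of the last dose.

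| Last dose (d) | Follow-up ends | Against one month (25-40) | Against three months (80-104) |
|---|---|---|---|
| -9 to -1 | day 21 to 29 | before nominal day 30 | not reached |
| 0 to 9 | day 30 to 39 | reaches day 30, ends before day 40 | not reached |
| 10 to 40 | day 40 to 70 | covers the window | not reached |

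The latest end is 40 + 30 = day 70, ten days before the three-month window opens.

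The first row mostly drops out of the analysis, because stops before SRS for a DLT or for steroids, and patients whose SRS was not delivered, are inevaluable and replaced. Among scored unblinded patients the one-month gap is therefore mainly the second row, and only when the MRI falls later than d + 30. For withdrawn patients the gap does not depend on timing, because steroid and MRI assessment is not required at all.

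**The plan's own figure.** Enumerating two independent Binomial(20) arms and declaring a go when the one-sided Fisher p-value is 0.30 or less gives power 0.802 for 75% against 50%; 9.5.2 states 0.80. The same rule has a true false-go probability of 0.215 at 50% against 50%.

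**Sensitivity of the decision.** Against 10/20 placebo successes, 12/20 gives p = 0.376 (no go) and 13/20 gives p = 0.262 (go). Near this boundary one patient's classification decides the result.

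**Effect of scoring unknowns as success.** Suppose a share m of an arm's outcomes is missing, unrelated to the outcome itself, and scored as success. That arm's apparent success rate becomes p + (1 - p)m. The values of m are assumptions; the documents give none.

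- No true effect, missing on glyburide only. With m = 5%, 0.5 + 0.5 × 0.05 = 0.525 and the false-go probability is 0.264. With m = 10%, the rate is 0.55 and the probability 0.318.
- No true effect, missing on placebo only. With m = 10% the probability falls to 0.134.
- No true effect, 10% missing in both arms: 0.214, essentially unchanged from 0.215.
- True rates 75% and 50%, 10% missing in both arms: the rates become 0.775 and 0.55, and power falls from 0.802 to 0.756.

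**Scoring unknowns as failure instead.** With no true effect and 10% missing on glyburide only, the probability becomes 0.134. That rule on its own moves the bias to the other side.

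**The case against.** Several stronger readings are tempting, and the documents do not support them.

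A reader might infer that any early stop leaves the primary outcome unobserved. It does not. Most stops before SRS lead to replacement, and with a last dose on or after SRS the follow-up always reaches nominal day 30. The 9.1.2 interval ends at the MRI, not at day 40, so an MRI on day 30 leaves no gap for an unblinded patient.

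A reader might infer that all three-month data are lost by rule. Section 7.6.3 takes patients off study treatment; it does not remove them from the protocol or cancel the visits in 4.2.7 and 4.2.8. Section 7.3.3 sits under toxicity reporting and can be read as a minimum. The visits may well take place. What stands is that the plan does not require them for these patients.

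A reader might infer a bias towards glyburide. Section 1.8 names hypoglycemia as the drug's most common side effect, so more unblinding on glyburide is plausible. But 7.6 also admits any extraordinary clinical circumstance, a hypoglycemia DLT stops drug without unblinding, and a life-threatening neurologic event could occur in either arm. No rate is given, and balanced losses cost power rather than bias the decision.

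It can also be said that 8.2.1 allows edema steroids only for symptomatic patients with increasing edema on imaging, so adverse-event follow-up would notice most cases. That is fair within the 30 days, but it does not make steroid status a required record and gives no cover afterwards. Finally, 9.1.2 says patients will be evaluated, so success by default is an inference from its last sentence. It is the natural inference, because no rule for unknown outcomes and no post-SRS ground for inevaluability is given.

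**Conclusion.** The mismatch is real and worth correcting, at the level of a recommended change. Required follow-up for unblinded and withdrawn patients never reaches the three-month endpoints; these are secondary, and 9.4 describes their analysis as largely graphical and descriptive. At one month the gap is narrow for unblinded patients. It is wider for withdrawn patients, whose steroid and MRI assessment is not required at all. As 9.1.2 is worded, an unobserved steroid start counts as success.

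The size depends on how many such patients there are and in which arm, which the documents do not say. The rise in the false-go probability shows what one-sided losses of 5% or 10% would do, assuming missingness unrelated to outcome and the one-sided Fisher test. It does not predict the trial's actual bias.

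**What to change.** In 7.6.3 and 7.3.3, separate stopping study drug from stopping outcome follow-up. Unblinded patients, and withdrawn patients who still consent to data collection, continue corticosteroid documentation and the one- and three-month visits and MRIs on the SRS-based schedule. Keep the 30-day adverse-event rule as a minimum. The rules for stopping drug are untouched.

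In 9.1.2, state that these patients remain evaluable and that success requires steroid status to be known through the one-month MRI. Report the primary test twice, with unknown outcomes scored as failure and as success, because either rule alone can favour one arm. At the same time reconcile 9.1.2 with 8.4.6, which defines the primary endpoint by MRI edema increase; under that definition a patient without a one-month MRI cannot be classified.

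The cost is protocol wording and a few more visits to track. Appendix VIII already marks the MRI, the history and physical, and steroid documentation as conventional care.

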8.0 SURGERY AND OTHER THERAPY

Intracranial surgery is not permitted on this study unless the intracranial surgical resection is of a lesion that leaves other intact lesions to be targeted with SRS and this surgery is completed prior to initiating glyburide or the investigational medication (which will be at least 5 days prior to SRS). There will be no SRS boost to the tumor bed of a resected lesion allowed. Extracranial surgery is permitted during the study at the discretion of the treating team.

8.1 Permitted Supportive Therapy

All supportive therapy for optimal medical care will be given during the study period at the discretion of the attending physician(s) within the parameters of the protocol and documented in each site's patient charts as concomitant medication.

- 8.1.1** Anticonvulsants: Anticonvulsants may be used as clinically indicated. Doses at study entry and at specific time points of the treatment must be recorded.
- 8.1.2** Antiemetics: Prophylactic antiemetics may be administered at the treating physician's discretion.
- 8.1.3** Cytotoxic chemotherapy is permitted at the discretion of the treating physician(s).
- 8.1.4** All further therapy that is not included in Section 8.2 is permitted at the treating physician's discretion, but should be recorded.

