1.0 INTRODUCTION

1.1 Background

Cerebral metastases affect ~10% of patients diagnosed with cancer. As techniques for local and systemic control of primary tumors improve, the incidence of brain metastases continues to rise. Vasogenic edema associated with brain metastases may result in significant neurologic defects resulting from mass effect. The standard treatment for symptomatic intracerebral edema is glucocorticoids. Administration of 4-8 mg of dexamethasone results in neurologic improvement in up to 75% of patients with brain metastases and significant edema. Dose-dependent toxic effects, such as myopathies, immunosuppression, hypothalamic/pituitary axis suppression etc., limit its long-term use. Other agents to reduce edema, including vascular endothelial growth factor (VEGF) inhibitors such as bevacizumab, show efficacy, but high cost and side effects limit use in most patients with malignancy-induced cerebral edema. The importance of finding an inexpensive, widely available, and well-tolerated agent, either to reduce edema associated with malignancy or to prevent development of edema in selected patients cannot be overstated (1).

Commonly prescribed glucose-lowering agents, especially sulfonylureas, have been of special research interest in preclinical and patient models with central nervous system (CNS)-related cytotoxic and malignant edema. Although in use as an oral hypoglycemic agent since the 1960s, glyburide (glibenclamide) has recently been rediscovered as a potential anti-edema agent. The utilization of glyburide to prevent neurologic deficits secondary to edema has been extensively described in preclinical models of ischemic stroke, subarachnoid hemorrhage, traumatic brain injury, and spinal cord injury. Retrospective studies examining diabetic patients with acute ischemic stroke have associated improved neurologic outcomes, decreased hemorrhagic transformation, and less mortality with glyburide administration. Recently published preclinical studies in mouse models with cerebral metastases have elucidated a potential benefit in prevention of edema using glyburide (2).

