1.8 Study Rationale

The most common side effect of glyburide is hypoglycemia. Sulfonylureas carry a rare but serious risk of increased cardiovascular mortality. Although the risk of cardiovascular mortality in patients receiving tolbutamide, a first-generation sulfonylurea, was 2.5 times that of patients treated with diet alone, subsequent studies have indicated that glyburide is not associated with an increased risk of cardiovascular events. A rare sulfonylurea-associated risk is hemolytic anemia in patients with G6PD deficiency and, in even more rare instances, in those without.

In contrast, dexamethasone causes disturbances in glucose metabolism in approximately 50% of patients, in addition to immunosuppression, femoral avascular necrosis, thrush, psychiatric disorders, and Cushing syndrome, among others.

In addition to a favorable side effect profile, the cost/benefit considerations of glyburide over alternatives merit consideration. The cost of a 30 day supply of glyburide is approximately \$30, compared with \$22 for dexamethasone. The cost of bevacizumab is approximately \$9,000/month.

Stereotactic radiosurgery (SRS) for brain metastases results in an approximately 5% incidence of radiation induced neurologic morbidity. Current interventional options include corticosteroids, pentoxifylline and vitamin E, surgery, hyperbaric oxygen, anticoagulation, and interstitial laser thermal therapy. More recently, bevacizumab has been shown to reduce T2/fluid-attenuated inversion recovery volumes on MR in patients with presumed SRS-induced radiation effects. A 90% improvement in neurologic symptomatology was noted; however, 61% of those patients experienced a return of neurologic symptomatology after discontinuation of anti-VEGF therapy. Because of the side-effect profile and high cost of anti-VEGF therapies, glyburide becomes an intriguing alternative as either prophylaxis against potential development of edema induced from radiotherapy or as a treatment alternative for existing edema that is at risk of becoming more significant with radiotherapy (1).

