3.2 Conditions for Patient Ineligibility

- 3.2.1** Known sulfonylurea treatment within 7 days prior to registration. Sulfonylureas include glyburide/glibenclamide (Diabeta, Glynase); glyburide plus metformin (Glucovance); glimepiride (Amaryl); repaglinide (Prandin); nateglinide (Starlix); glipizide (Glucotrol, GlibeneseR, MinodiabR); gliclazide (DiamicronR); tolbutamide (Orinase, Tolinsase); and glibornuride (Glutril).
- 3.2.2** Diffuse Leptomeningeal metastases.
- 3.2.3** Known allergy to sulfa or specific allergy to sulfonylurea drugs.
- 3.2.4** Use of VEGF inhibitors within 10 days prior to registration.
- 3.2.5** Allergy to gadolinium.
- 3.2.6** Type 1 diabetes mellitus or Type 2 diabetes mellitus actively receiving treatment.
- 3.2.7** Cognitive impairment that precludes a patient from acting as his or her own agent to provide informed consent.
- 3.2.8** Concurrent use of Bosentan.
- 3.2.9** Any major medical illnesses or psychiatric impairments that in the treating physician's opinion will prevent administration or completion of protocol therapy (which may include patients who are elderly, debilitated, or malnourished persons and/or those with renal, hepatic or adrenal insufficiency).
- 3.2.10** Pregnant or breast feeding women due potential damage to the fetus.
- 3.2.11** Inability to undergo MRI or SRS (e.g. due to safety reasons such as presence of a pacemaker).
- 3.2.12** Deemed by the treating physician to be unable to eat regular meals.

3.2.13 Patients currently on beta blockers.

3.2.14 Patient with a known diagnosis of ongoing alcoholism/alcohol abuse.

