8.2 Non-Permitted Supportive Therapy

- 8.2.1** Corticosteroids: Dexamethasone (or any other corticosteroid whose purpose is to treat cerebral edema) should only be administered if the patient is clinically symptomatic, has imaging demonstrating increasing cerebral edema, and is deemed by the treating physician to require dexamethasone (or another corticosteroid). If administered between SRS and the one month follow-up MRI, these patients will be recorded as a treatment failure (primary endpoint). If initiated prior to SRS, this is criteria for withdrawal from the protocol, these patients would be deemed inevaluable. If initiated after the one month follow-up MRI, the dose, value, and reason will be recorded. Low dose prednisone or other non-dexamethasone steroids are allowed as long as they are not administered with the intent of treating cerebral edema.

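### Under 9.1.2, edema treated before the one-month MRI only with a non-steroid agent, such as a VEGF inhibitor, is scored as a treatment success; likely uncommon, but cheap to close

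*Combined protocol and SAP*

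**What the plan says.** **What may be given.** Section 8.1.4 reads: "All further therapy that is not included in Section 8.2 is permitted", at the physician's discretion and provided that it is recorded. Section 8.2 has one entry, corticosteroids given for cerebral edema. Of those it says: "If administered between SRS and the one month follow-up MRI, these patients will be recorded as a treatment failure (primary endpoint". VEGF inhibitors appear as a restriction only among the exclusions, in 3.2.4: "Use of VEGF inhibitors within 10 days prior to registration". Nothing restricts them after registration. Section 8.0 deals with surgery separately: "Intracranial surgery is not permitted on this study unless" the resection leaves other lesions for SRS and is finished before study drug starts.

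**What the authors say about these agents.** Section 1.1: "Other agents to reduce edema, including vascular endothelial growth factor (VEGF) inhibitors such as bevacizumab, show efficacy". Section 1.8: "bevacizumab has been shown to reduce T2/fluid-attenuated inversion recovery volumes on MR in patients with presumed SRS-induced radiation effects".

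**How outcome is scored.** Section 9.1.2 recognises two failures between SRS and the one-month MRI: edema that requires a corticosteroid, and a death probably or likely related to glyburide. It then closes: "Otherwise, the patient will be considered to have experienced treatment success". Section 8.4.6 instead defines the randomized primary endpoint by edema increase on imaging, and 2.3.2 joins edema increase and corticosteroid initiation with "and" wording. None of the three says how edema treated with something other than a steroid is to be scored.

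**The concern.** The trial asks whether glyburide prevents clinically important edema after SRS. A patient whose edema is bad enough to be treated has had the event of interest, whichever agent is used. Section 9.1.2 scores the agent rather than the event, so treatment with a non-steroid agent alone turns a would-be failure into a success.

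Such treatment follows symptoms, so it should fall more often in the arm with more edema. If glyburide works, that is the placebo arm, and the observed difference shrinks. The screening decision in 9.3.2 would then lean towards dropping an agent that deserves further study. The entry exclusion in 3.2.4, and the statements in 1.1 and 1.8, show that the authors knew these agents act on the outcome.

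A related but separate matter is a VEGF inhibitor given as cancer treatment. It would not affect 9.1.2 directly, since that definition has no volume threshold. It could lower the FLAIR volumes used in 8.4 and in the fourth randomized secondary endpoint (9.2.2).

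**Working it through.** **Inputs from the documents.** 20 patients per arm; exact test of proportions, one-sided, p of 0.30 or less (9.3.2). Success 50% on placebo and 75% on glyburide, power 0.80 (9.5.2).

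**Assumed input.** f is the share of would-be failures treated for edema without any steroid. The documents give no value. I take f equal in both arms and show 2% to 30%.

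**Step 1: the plan's own figure.** Enumerating both binomials (n = 20) with a one-sided Fisher exact test at p ≤ 0.30 gives power 0.802, which matches the stated 0.80. The actual type I error at 50% in both arms is 0.215.

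**Step 2: effect of the scoring rule.** Observed success in each arm is p' = p + f(1 − p). The observed difference is therefore 0.25 × (1 − f). The design expects 20 × 0.50 + 20 × 0.25 = 15 failures, so f corresponds to 15f patients.

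| f (assumed) | Patients rescored | Placebo | Glyburide | Power | Type I error* |
|---|---|---|---|---|---|
| 0 | 0 | 50% | 75% | 0.802 | 0.215 |
| 2% | 0.3 | 51% | 75.5% | 0.793 | 0.215 |
| 5% | 0.75 | 52.5% | 76.25% | 0.780 | 0.214 |
| 6.7% | 1 | 53.3% | 76.7% | 0.772 | 0.214 |
| 10% | 1.5 | 55% | 77.5% | 0.756 | 0.214 |
| 20% | 3 | 60% | 80% | 0.704 | 0.210 |
| 30% | 4.5 | 65% | 82.5% | 0.645 | 0.203 |

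*Both arms at a true success rate of 50%, the same f in each.

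**Step 3: one patient.** With 13 successes on glyburide against 10 on placebo, p = 0.26 and the rule says continue. Rescore one placebo failure as a success, giving 13 against 11, and p = 0.37, so the rule says stop. At the design rates, moving one placebo failure to success reverses a positive decision in about 10.5% of trials.

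**Step 4: the same patient under each definition** (edema treated after SRS and before the one-month MRI, with a non-steroid agent only).

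- 9.1.2: success.
- 8.4.6: failure if the one-month MRI still meets the increase criterion in 8.4.4 or 8.4.5; success only if it no longer does.
- 2.3.2: not an event, because no corticosteroid was started.

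**The case against.** **It will be rare.** This largely stands. The scenario needs a patient treated for edema within about a month of SRS with no steroid at all, since any steroid given for edema in that window already scores failure. Section 1.1 calls glucocorticoids the standard treatment and says cost and side effects limit VEGF inhibitors in most patients. Section 1.8 puts bevacizumab at about $9,000 a month against $22 for dexamethasone. The lower rows of the table are the plausible ones; 20% or 30% would mean 3 to 4.5 of about 15 failures.

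**It depends on which endpoint applies.** This stands too. Under 8.4.6 the patient may still fail. But 9.1.2 is the definition that is analysed and powered, and the conflict between sections does not close the gap.

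**Edema need only be severe enough to require a steroid, so 9.1.2 could be read as need rather than use.** This does not stand: 8.2.1 scores failure on administration of the steroid.

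**One patient can flip any borderline result in 40.** True, and not specific to this issue. It is a reason to remove avoidable misclassification, not evidence of a large effect.

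A reader might also infer three stronger things that the documents do not support:

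- That every option listed in 1.8 is an unscored edema rescue. That list concerns radiation-induced neurologic morbidity, put at about 5%, and intracranial surgery after study drug starts is already barred by 8.0.
- That the rule favours glyburide. A false-positive excess would need more such use on glyburide than on placebo (with no true effect, 20% of failures on glyburide and none on placebo raises the error from 0.215 to 0.439). Nothing in the documents points that way, and treatment is blinded.
- That cancer-directed VEGF inhibitors bias the 9.1.2 comparison through FLAIR volume. Volume does not enter 9.1.2, and randomization guards against imbalance in background therapy.

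**Conclusion.** The scoring gap is real. Under 9.1.2 a patient whose edema is treated only with a non-steroid agent between SRS and the one-month MRI is a success; under 8.4.6 that patient escapes failure only if the increase has gone by the MRI.

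The expected effect is small. At 2% to 10% of would-be failures, power falls by about 1 to 5 percentage points (0.802 to between 0.793 and 0.756). Larger losses need rates that the documents make unlikely. With the Fisher test and equal rates in both arms, type I error does not rise. All of this rests on assumed rates, the 50% and 75% success rates of 9.5.2, and equal f in both arms. If such use were concentrated in the placebo arm the loss would be larger: 20% of placebo failures only (60% against 75%) gives power 0.570.

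It is worth correcting because the rule misclassifies the event under study, the decision can turn on one patient, and the correction is cheap. It does not invalidate the design or the sample size.

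**What to change.** 1. In 9.1.2, and in the same words in 2.3.2 and 8.4.6, score the start of any therapy given to treat cerebral edema between SRS and the one-month MRI as treatment failure. Changing 9.1.2 alone would leave the definitions in conflict.
2. For such therapy, record the start date and the reason, as sections 4.2.6 and 4.2.7 already require for new corticosteroids. Section 8.1.4 now asks only that other therapy be recorded.
3. Flag patients given a VEGF inhibitor for any other reason, and add a sensitivity analysis of the primary outcome and the FLAIR volume endpoints that takes account of them.

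This changes scoring only, not what may be given, and leaves the planned 20 per arm unchanged. The cost is a start-date and reason field, and a judgement of intent for agents that serve two purposes. That judgement should be made blind to assignment.
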